research object	Gene screening data of 40,000 newborns (138 genes related to 133 common genetic diseases) and tandem mass spectrometry data (11 amino acids and 28 acylcarnitines).
Inclusion criteria	(1) Newborns who underwent genetic screening and tandem mass spectrometry at the same time. (2) Age : 0-28 days, gestational age 37-42 weeks.
Excluded criteria	Data that meets any of the following conditions need to be eliminated : (1) Neonatal data with unclear clinical basic information ; (2) Lack of traceability core information data ; (3) The data that the test results cannot be analyzed and interpreted.
sample size	Gene screening and tandem mass spectrometry data of 40,000 newborns.
data collection	(1) Basic information : gender, age, sample type, subject traceability number / ID number, etc. (2) Clinical symptoms, biochemical and imaging data of positive samples. (3) Gene detection results and tandem mass spectrometry results.

	(4) Date of test data, instrument model, reagent type, etc.
Statistical processing	IBM-SPSS 26.0 statistical software was used to analyze the test results. Logistic regression analysis was used to evaluate the correlation between genotype and clinical phenotype. Generalized multifactor dimensionality reduction method was used to analyze gene-gene interaction and genotype-phenotype correlation. Based on tandem mass spectrometry data, machine learning algorithms such as random forest, support vector machine, elastic network, and multi-layer perceptron were used to construct a genotype prediction model. The prediction effect of the model was evaluated by accuracy, balance accuracy, sensitivity, and specificity.
abbreviation	Principal Investigator, PI; tandem mass spectrometry, MS/MS; Inborn errors of metabolism, IEM

1. project basis

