model was applied to the diagnosis of common pediatric diseases. The results showed that the diagnostic accuracy of 55 common pediatric diseases was close to 90 %. Some diseases such as acute upper respiratory tract infection had a diagnostic accuracy of 95 %, and the average score of the artificial intelligence model was higher than that of the doctor group. Therefore, artificial intelligence can assist early disease diagnosis through a large amount of medical data, improve diagnosis efficiency and reduce misdiagnosis rate, solve the problem of insufficient medical service capacity to a certain extent, and improve the fairness and accessibility of health services. In the field of neonatal disease screening, with the promotion of genetic screening technology and the inclusion of more genetic metabolic diseases in screening, accurate and rapid judgment of multiple disease risks has become an urgent need for clinical front-line. Artificial intelligence has obvious advantages in the interpretation and risk prediction of genetic metabolic disease gene results, which not only significantly reduces the false positive results and saves medical resources ; for areas with weak clinical foundation and urgent need to carry out neonatal genetic metabolic disease gene screening projects, artificial intelligence tools will become a strong support for clinicians, promote the standardization and standardization of genetic metabolic disease diagnosis, and improve the efficiency and accuracy of neonatal genetic metabolic disease gene screening system.

According to the preliminary development of neonatal genetic screening in China, we will retrospectively collect and analyze the genetic screening data and tandem mass spectrometry data of 40,000 newborns in the participating units of the South China Neonatal Genetic Screening Alliance, so as to understand the incidence of neonatal genetic diseases in China and the characteristics of the carrying rate and mutation sites of related gene pathogenic variations, and provide scientific research basis for the feasibility, clinical value and social benefits of large-scale genetic screening. In addition, our previous studies have found that the mutation sites with high carrying rate (more than 1 %) in many populations are mutations of unknown clinical significance (VUS). The pathogenic interpretation of such mutations has brought serious confusion to clinicians and brought pending trouble to the subjects.

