How to accurately analyze the pathogenicity of a large number of high-frequency VUS mutations has become a key problem to be solved in neonatal genetic screening. Therefore, we intend to use 40,000 cases of gene screening data and tandem mass spectrometry data, and establish a risk assessment model for neonatal genetic metabolic disease gene screening results through protein function artificial intelligence method, in order to solve the pathogenicity problem of high-frequency VUS and provide reliable research basis for clinical practice, so as to quickly and accurately identify high-risk children, reduce the false positive rate of gene screening, and improve the accuracy and system efficiency of neonatal gene screening.

In addition, we will also explore the use of neonatal gene screening data and tandem mass spectrometry data, as well as machine learning algorithms such as random forest, support vector machine, elastic network, and multi-layer perceptron to construct prediction models for common genetic diseases, and strive to achieve accurate diagnosis and prediction of common genetic diseases using simple tandem mass spectrometry metabolomics data, and expand the application range of tandem mass spectrometry technology for disease detection.

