1.2 Creativity

This study is a multi-center cooperative study of the South China Neonatal Genetic Screening Alliance. Through the analysis of 40,000 cases of neonatal genetic screening data and MS / MS data, the incidence of common genetic diseases in newborns in China and the carrying rate of related gene pathogenic mutations are deeply understood, and the types of diseases, gene selection, gene screening process, interpretation of gene screening results, follow-up and treatment of screening positive patients and other related contents of neonatal genetic screening are preliminarily clarified, so as to provide scientific research basis for the feasibility, clinical value and social benefits of large-scale genetic screening.

In addition, this study will clarify the correlation between genotypes and metabolic profiles of common genetic diseases in newborns, and explore the feasibility of using protein function artificial intelligence analysis platform and tandem mass spectrometry metabolite data to accurately predict the pathogenicity of

ectopic sites of genetic metabolic lesions through protein function prediction and metabolic level analysis of high-frequency mutation sites of genes, that is, to solve the pathogenicity of mutations with unknown clinical significance. It will also expand the types of disease diagnosis of neonatal MS / MS technology.

This study will also establish a risk assessment model for neonatal genetic metabolic disease gene screening results through artificial intelligence methods. By identifying the pathogenicity of mutation sites, especially those with unclear clinical significance, it can quickly identify high-risk children and reduce false positive rates, thereby improving the accuracy and system efficiency of neonatal genetic screening.

2. Research objective

(1) Gene sequencing data (138 genes related to 133 common genetic diseases) and tandem mass spectrometry metabolomics data (11 amino acids and 28 acylcarnitines) of about 40,000 newborns from the South China Neonatal Genetic Screening Alliance participating units were collected and collated to complete the database construction of genes and mass spectrometry.

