model were established. Construction and selection of modeling indicators, select core indicators through information gain and correlation coefficient, and construct combined features ; in the model training stage, the gene screening data is divided into training set and test set at a ratio of 8 : 2, and the ensemble learning models such as random forest, gradient boosting tree algorithm and artificial neural network are trained to select the best model. Model evaluation, the model selection process first meets the detection rate of 1, and then compares the false positive rate to select the optimal training model. Model verification, using a new batch of big data samples, through model calculation, output high-risk and low-risk sample lists, and compare and analyze with the original screening results.

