3.6 Observation items

(1) Positive detection rate of common genetic diseases in neonates : the results of genetic testing of enrolled neonates showed that the proportion of homozygous and compound heterozygotes of autosomal recessive inheritance, single heterozygote and homozygous of autosomal dominant inheritance, and hemizygote of X-linked inheritance accounted for the total number of people tested.

(2) The corresponding pathogenic genes and pathogenic variation carrying rate of common neonatal genetic diseases : that is, the proportion of the total number of occurrences of pathogenic variation, suspected pathogenic variation and

unknown clinical significance variation in the genetic test results of the enrolled neonates according to the ' ACMG genetic variation classification criteria and guidelines ' and ' genetic variation classification criteria and guidelines (2017) '.

- (3) The carrying rate of high-frequency mutation sites in the population : that is, the mutation sites with a population carrying rate greater than 1 %.
- (4) Establish a complete protein structure and catalytic activity analysis process, and develop artificial intelligence protein analysis tools for pathogenicity prediction of mutation sites.
- (5) Preliminary identification of the pathogenicity of high-frequency VUS mutation sites : The protein structure and enzyme catalytic activity characteristics of high-frequency VUS mutation sites were predicted by artificial intelligence tools, and the metabolic spectrum differences between positive, carrier and negative samples of high-frequency VUS mutation sites were clarified by combining with tandem mass spectrometry metabolite data, which provided a basis for the pathogenicity judgment of VUS mutation.
- (6) Gene-metabolism correlation : machine learning algorithms such as random forest, support vector machine, elastic network and multi-layer perceptron are used to construct prediction models of common genetic diseases, so as to realize accurate diagnosis of common genetic diseases through tandem mass spectrometry metabolomics data, and expand 2-3 diseases that can be diagnosed by tandem mass spectrometry.

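### As written, the 8:2 split puts recurrent variants in both training and test sets, so the test cannot show that the risk model judges a variant it has not seen

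*Combined protocol and SAP*

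**What the plan says.** Section 3.3 (data collection), item (4) describes the risk model. Features are selected, then "the gene screening data is divided into training set and test set at a ratio of 8 : 2", several ensemble and neural-network models are trained, and the best is chosen by requiring a detection rate of 1 and then comparing false positive rates. A verification step follows: a further batch of samples is run through the model to "output high-risk and low-risk sample lists", and these lists are compared with the original screening results.

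The Abstract gives the research object as "Gene screening data of 40,000 newborns", together with their mass spectrometry data. No section mentions grouping by variant or gene when the data are split.

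The model's purpose is stated at variant level. Section 1.1 says it is built "in order to solve the pathogenicity problem of high-frequency VUS". Section 1.2 says: "By identifying the pathogenicity of mutation sites, especially those with unclear clinical significance, it can quickly identify high-risk children and reduce false positive rates". Section 3.6, item (3) defines high-frequency sites as "the mutation sites with a population carrying rate greater than 1" per cent.

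Section 3.3, item (2) counts only pathogenic and likely pathogenic (P/LP) variants as positive. It defines disease-positive newborns by zygosity and mode of inheritance, and does not let a VUS serve directly as the basis for diagnosis.

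**The concern.** The claim is about variants and the test is about babies. Variant-level inputs, such as the variant's identity, its gene or a predicted protein-function score, are the same in every carrier. If carriers of one variant sit in both sets, a model can do well in the test partly by recalling what it was told about that variant in training. A good test result would then not distinguish a model that has learned what makes a variant harmful from one that has learned a list.

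For a baby carrying an already classified variant, the list may be enough. For a VUS there is no entry to recall, and that is where sections 1.1 and 1.2 expect the model to help. If the 8:2 result were offered as evidence for VUS calls, it would answer a different question from the one asked.

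**Working it through.** The plan gives no overlap figure to reproduce, so the check starts from its own inputs.

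**Inputs.** 40,000 newborns (Abstract). Ratio 8:2 (section 3.3, item (4)), hence 32,000 in training and 8,000 in test if newborns are the unit. High-frequency threshold 1% (section 3.6, item (3)), hence 0.01 × 40,000 = 400 carriers. Assumption: newborns are allocated at random, with no grouping.

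**Step 1: a site at the threshold.** Expected carriers in training: 0.8 × 400 = 320. In test: 0.2 × 400 = 80, with a 95% range of 65 to 96 (hypergeometric). The chance that all 400 fall in one set is about 1e-39.

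**Step 2: rarer variants.** For a variant with k carriers, the chance that it appears in both sets is 1 − 0.8^k − 0.2^k; the exact hypergeometric values agree closely. Given one carrier in the test set, the variant is missing from training only if the other k − 1 carriers are also in test. The chance that a test carrier's variant was also in training is therefore 1 − 0.2^(k−1).

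| Carriers k | Variant in both sets | Test carrier's variant also in training |
|---|---|---|
| 1 | 0 | 0 |
| 2 | 0.32 | 0.80 |
| 3 | 0.48 | 0.96 |
| 5 | 0.67 | 0.998 |
| 10 | 0.89 | effectively 1 |
| 40 | 0.9999 | effectively 1 |
| 400 | 1.000 | effectively 1 |

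**Step 3: the mechanism, by illustration.** Assumptions, none from the plan: 50 variants, each given a random label (30% positive) shared by all its carriers, and a model that only memorises variant identity and otherwise predicts the majority class. Under a record-level 8:2 split its balanced accuracy is 0.91 with 2 carriers per variant and 1.00 with 5 or more. With whole variants held out it is 0.50, which is chance. The model has no skill on a new variant, and only the second split reveals it. These values show how the overlap works; they do not estimate accuracy in this study.

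**Step 4: the verification batch.** It brings new babies but reserves no variants. A site above 1% will recur in any large batch from the same population. The comparator is the original screening results. If these follow section 3.3, item (2), a VUS carries no positive label there. This step therefore has the same limit as the 8:2 test.

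**The case against.** Several points on the other side stand.

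- **The unit is not stated.** A reader might infer that the plan prescribes a newborn-level split. It does not; that reading comes from the form of the data and of the output. What can be said is that, as written, nothing prevents the overlap.
- **Not every variant overlaps.** A variant with a single carrier cannot be in both sets.
- **The illustration is not this study.** A reader might infer that a worthless model would pass here with near-perfect figures. The documents do not support that. Disease-positive status in section 3.3, item (2) depends on zygosity and inheritance as well as on the variant. Assuming Hardy-Weinberg proportions and a recessive site with allele frequency 0.005, 40,000 newborns give 2 × 0.005 × 0.995 × 40,000 = 398 heterozygotes and 0.005² × 40,000 = 1 homozygote, and variant identity alone cannot separate them. Mass spectrometry values also differ between carriers, and a model that relied on them would memorise less. But the plan does not confine the inputs to such values, and a record-level test cannot tell which route a model took.
- **VUS have another line of evidence.** Section 3.6, items (4) and (5) address high-frequency VUS through protein-structure and catalytic-activity prediction and metabolic comparisons, and call the result preliminary. A reader might infer that all the VUS work rests on the 8:2 test, which is not so. Sections 1.1 and 1.2 nevertheless assign VUS pathogenicity to the risk model too, and the plan gives that model no other test.
- **Grouping alone is not enough.** The risk model's outcome is never defined. If it simply restates the P/LP rule, no split can validate a VUS call. Compound heterozygotes also link two variants in one record, which complicates grouping. Both points shape the remedy but do not remove the concern.

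**Conclusion.** The point holds in limited form. If the 8:2 split is made on newborns without grouping, essentially every site above 1% is in both sets (about 320 and 80 carriers at the threshold), and a test carrier's variant has very probably been seen in training even when only a few babies carry it. The test and the later verification can support a claim about new babies with already classified variants. They cannot support the claim that the model judges variants of unseen status.

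The size of the overlap rests on random allocation at newborn level, which is inferred. The effect on reported accuracy is not known: it depends on the inputs and the outcome, and the plan fixes neither. A reader might infer that the 8:2 test is invalid altogether; it is not, for the narrower claim. This is an inexpensive improvement that matters because it concerns a stated aim of the model.

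**What to change.** 1. State the splitting unit. Keep the newborn-level 8:2 split and label its result as performance in new babies carrying already classified variants.
2. Define the risk model's outcome, so that it does not simply restate the variant's P/LP class. The confirmed-case data in section 3.3, item (3) are one candidate. Those records include gene detection information, so the definition should say which biochemical and clinical findings establish the case.
3. Add a grouped cross-validation that holds out whole classified variants, with all carriers of a variant on the same side. Variants that occur together in a compound heterozygote go in the same group; if the groups become unwieldy, hold out whole genes. Repeat feature selection and model choice within each training part.
4. Base any statement that the risk model predicts VUS pathogenicity on the grouped result only.

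No new data collection is needed beyond the items the plan already lists. The costs are reported accuracy that will probably be lower, a split ratio that is only approximate, and extra analysis work to define the outcome and form the linked groups. The plan does not give the number of confirmed cases, so the precision of the grouped result cannot be stated in advance and should be reported with an interval.

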0.001-0.01), benign (B, pathogenic possibility < 0.001). The results of gene detection in this study only classified pathogenic and possible pathogenic mutations as positive mutations, and homozygotes and compound heterozygotes of autosomal recessive inheritance, single heterozygotes and homozygotes of autosomal dominant inheritance, and hemizygotes of X-linked inheritance were classified as disease positive. The unclear clinical significance is not directly used as the basis for clinical diagnosis. It is necessary to combine the clinical, if necessary, to carry out the corresponding family member verification, auxiliary examination, clinical follow-up.

(3) MS / MS data collection and standardization : The collected data include (1) laboratory background information including instrument type, reagent type, quality control material type, laboratory quality control rules, filter paper type, normal population range ; (2) Quality control data included quality control number, quality control type, quality control batch number, amino acid internal standard batch number, acylcarnitine internal standard batch number, factory time, experimental time, and test value of each quality control analyte ; (3) Screening test data include screening number, gestational age, breastfeeding method, native place (province, city), newborn gender, birth date, birth weight, sample number, blood collection time, etc. ; (4) The data of confirmed cases included screening number, confirmed disease, blood ammonia test, blood gas analysis, blood routine, liver function test, urine GC-MS test, imaging examination, gene detection information and other tests. The fluctuation range of the detection concentration of the corresponding batch of quality control samples was within the target value ± 3 s. Finally, the data were collected and sorted into the negative database and the positive database. In order to eliminate the influence of regional differences, the series detection index data were standardized.

(4) By analyzing the correlation between large sample gene data and tandem mass spectrometry data and the correction of clinical prognosis, a neonatal genetic disease gene screening database and an artificial intelligence risk assessment

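### The rule of detection rate 1, then lowest false-positive rate, is not tied to the training or the test data; choosing by cross-validation and using the test set once is a cheap improvement

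*Combined protocol and SAP*

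**What the plan says.** Section 3.3 (data collection), item (4), describes the risk model in four steps.

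- **Indicators:** "select core indicators through information gain and correlation coefficient, and construct combined features".
- **Training:** "the gene screening data is divided into training set and test set at a ratio of 8 : 2", after which random forest, gradient boosting and a neural network are fitted.
- **Evaluation:** "the model selection process first meets the detection rate of 1, and then compares the false positive rate to select the optimal training model".
- **Verification:** "Model verification, using a new batch of big data samples", from which the model is to "output high-risk and low-risk sample lists" and then "compare and analyze with the original screening results".

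The section names no data set for the selection rule, no cross-validation, no cut-off rule and no interval. The size and source of the new batch are also not given.

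Item (3) of the same section says that "the data were collected and sorted into the negative database and the positive database". It also collects confirmed diagnoses: "The data of confirmed cases included screening number, confirmed disease", with further tests.

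The MS/MS models (random forest, support vector machine, elastic net, multilayer perceptron) are described separately in 3.1 Research Design, 3.6 item (6) and 3.7. Section 3.7 lists accuracy, balanced accuracy, sensitivity and specificity as measures. No split, resampling or interval is stated for these models, and section 5 says only that the work will be verified.

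**The concern.** A selection rule means something only once the data it is applied to are named, and here either choice has a drawback.

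On the training data, a model that can memorise its input meets the rule perfectly whether or not it has learned anything. The rule then rewards flexibility and can prefer a model that is no better, or is worse, in new newborns.

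On the test set, every model that passes has sensitivity 1 there by definition. That figure cannot also be reported as an independent estimate, and only the new batch could supply one.

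The study aims at accurate diagnosis from MS/MS and at adding 2-3 diseases that MS/MS can detect. Individual diseases may have few cases. Perfect detection in a handful is weak evidence, and without an interval a reader cannot see that.

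**Working it through.** The plan gives no performance or precision figure, so there is none to reproduce.

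**Inputs.** The sample is 40,000 newborns and the split is 8:2, so 32,000 train and 8,000 test if all are used. No positive rate is given for this panel. As assumptions I take three rates from 1.1 Research background: 2.3% and 4.0% (other panels) and 8.81% (the team's pilot, as printed). The printed pilot counts give 158/1739 = 9.09%, which would mean 727 test positives instead of 705 and changes no conclusion.

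**1. Training-data reading.** Simulation: 40,000 newborns, 920 positives (2.3%), 39 continuous predictors of pure noise, cut-off at the lowest-scoring training positive. The plan states no cut-off, so this one is an assumption.

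- Random forest, 7 runs (one adding 138 sparse gene indicators): training detection 1 and false-positive rate 0 in all; test AUC 0.48-0.52.
- Boosting with 400 rounds, 2 runs: also detection 1 and false-positive rate 0.
- Boosting with 100 rounds, 1 run: false-positive rate 0.167 at detection 1. The problem is therefore confined to models that can fit perfectly.
- With real signal in 3 of the 39 predictors (0.5 or 1.0 SD, assumed), the rule chose random forest over 100-round boosting in 10 of 10 runs. The forest's test AUC was lower in 9 of 10, by 0.002-0.07.

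**2. Test-set reading, one pooled model.** Expected test positives are 8,000 × 0.023 = 184, 8,000 × 0.04 = 320 and 8,000 × 0.0881 ≈ 705. If the cut-off is the lowest score among n test positives, expected sensitivity in new data is n/(n+1). Taking the lowest false-positive rate among K = 3 equally good, independent models lowers it further (simulated, normal scores 2 SD apart). Models scored on the same newborns are correlated, so the truth lies between the two columns. The exact 95% lower limit for n of n detected is 0.025^(1/n), which is valid only if the test set played no part in selection.

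| Test positives | K = 1 | K = 3 | Lower limit for n/n |
|---|---|---|---|
| 184 | 0.995 | 0.990 | 98.0% |
| 320 | 0.997 | 0.994 | 98.9% |
| 705 | 0.999 | 0.997 | 99.5% |

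The optimism is therefore at most about 1 point.

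**3. Only if selection or claims are made per disease.** Spread evenly over 133 diseases, the test positives are 184/133 = 1.4, 320/133 = 2.4 or 705/133 = 5.3 each; real counts will be uneven. With 5 positives, expected new-data sensitivity is 5/6 = 0.83 for K = 1 and about 0.71 for K = 3, against an apparent 1. Even in an untouched test set, the lower limit is 0.025^(1/5) = 47.8% for 5/5, 63.1% for 8/8 and 83.2% for 20/20. A lower limit of at least 90% needs 36/36.

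**4. Would the same rule work on cross-validated predictions?** Not well. Under the signal in step 1, an ideal score separates the groups by √3 × 0.5 = 0.87 or √3 × 1.0 = 1.73 SD. The lowest of the 736 training positives (0.8 × 920) lies on average about 3.15 SD below their mean. A cut-off there gives an average false-positive rate of about 98% or 91%. The ranking then hangs on one worst-scoring newborn.

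**The case against.** The strongest reply is that item (4) lists training, evaluation and verification as separate steps, so evaluation most naturally means the 20% test set. On that reading the pooled optimism is small and a new batch follows. The models are also presented as exploratory. All of this stands, and it keeps the point to an inexpensive improvement. It does not make a sensitivity fixed at 1 an independent estimate, and it does not say where the new batch comes from.

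Four stronger readings are tempting and are not supported:

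- **The 8:2 split is the only safeguard.** The same item plans verification on a new batch. The gap is its source and its comparator. Comparing with the screening results also does not exclude use of the confirmed diagnoses.
- **A model chosen on training data would miss nearly all new cases.** That follows mainly from placing the cut-off at the lowest training positive, which the plan does not state. With both models set to 5% test false positives, sensitivity was nearly the same: 10.3-17.4% for the forest against 10.9-14.1% for boosting at 0.5 SD, and 39.7-46.2% against 40.2-46.2% at 1.0 SD. The simulated predictors also resemble the MS/MS panel more than the gene data that item (4) splits.
- **Sensitivity will be badly inflated for each disease.** One positive and one negative database, with high- and low-risk lists, point to one pooled model. Nothing says that the rule is applied per disease or that it governs the MS/MS models.
- **Feature selection leaks test data.** It is listed before the split, but clause order does not establish the workflow.

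**Conclusion.** The point holds as a cheap improvement worth making. The plan does not say which data the selection rule uses. On training data it favours models that fit perfectly and can pick one that is no better or is worse. On the test set it fixes sensitivity at 1.

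For one pooled model the second effect is under about 1 point, assuming at least 184 test positives. It becomes large (expected sensitivity about 0.71-0.83 with 5 positives) only under per-disease selection, which is an assumption. The size of the training-data effect rests on simulated predictors and signal, so only its direction should be relied on.

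The missing split and interval for the MS/MS models, and the unstated source of the new batch, do not depend on any of these assumptions.

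**What to change.** In 3.3 item (4) and 3.7:

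1. Choose features, algorithm and cut-off by cross-validation within the 80% training data.
2. Compare models there by false-positive rate at a common, pre-stated high detection rate, or by the whole ROC curve. Exact detection of 1 depends on the single worst-scoring positive.
3. Lock the model and evaluate it once on the untouched 20%, then on the new batch. Name the source of that batch in advance, for example later months or whole hospitals.
4. Evaluate against confirmed disease status where available, as well as the screening results.
5. Apply the same steps to the MS/MS models. For each disease claimed as newly detectable, report the held-out case count, sensitivity with exact 95% interval, and false-positive rate.

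The cost is about a paragraph of text and some computing time. The 8:2 split stays and no new data are required. The downsides are less favourable figures, and a smaller development set if the batch has to be set aside from the 40,000.
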